We will ask two screening centres (Northeast & Cumbria and one other) centres to provide names, addresses of a random sample of men in surveillance to the research team using processes described in the previous survey section. The research team will send written information (covering letter, PIS, consent form, reply paid envelope) and then arrange for a telephone call to those who reply to administer the questionnaire.

Sample size

Based on previous experience with telephone surveys with vascular patients, where an approximate 60% response rate was achieved, we expect we will need to contact 500 men to achieve 300 responses (Michaels et al 2021). The sample size is based on precedence, where the literature shows that the majority of DCE sample sizes range between 100 and 300 (de Bekker-Grob 2015). Precedence is used because sample size calculations are difficult to estimate *a priori* without knowing the number of attributes and levels that will be included in the DCE. Based upon the CV literature and previous experience with the technique (Lin 2013, Shackley and Dixon 2014), a sample of 300 will be sufficient for meaningful analysis of WTP data.

Data collection

The telephone survey will be administered by the Research Associate with support from the Qualitative Researcher if necessary. Men will be asked to give verbal consent prior to the questionnaire being administered. We expect each telephone call to last no more than 20 minutes, based on our previous study where the average interview time was 13 minutes (Wickramasekera 2019).

Analysis

For the DCE, choice data will be modelled using a conditional logic model. Regression coefficients will be used to estimate the relative importance of attributes and the marginal rates of substitution will be calculated (i.e. trade off preferences for Exit Strategy characteristics) (de Bekker-Grob 2012). Latent class models will be used to analyse individual heterogeneity and to identify subsets of patients with

varying preferences (Hole 2016). For CV, the relative strength of men's preferences for the strategies will be estimated from calculating mean and median WTP values and testing for differences by using t-tests and Mann–Whitney U tests. Multivariate regression analyses will be performed to examine possible determinants of stated WTP and determine how WTP varies by different group characteristics. We will consider the use of a weighted sample here to address non-response bias.

PS has considerable experience of both DCE and CV studies, as well as preference elicitation studies more generally (Shackley & Dixon 2014, Rowen 2016). Whichever method is used, the results will identify whether preferences differ by factors such as age, size of AAA, rate of AAA growth (men are given the size of their AAA in writing at each screening attendance), social deprivation, general health, ethnicity, and disability. This will help NAAASP to develop an Exit Strategy and/or a decision aid for exit that is patient focused. The results can also feed into future cost-effectiveness modelling of Exit Strategies by considering men's preferences alongside costs and effectiveness.

3. Integration of qualitative interviews and survey

This is a sequential study where findings from one phase inform the content of the next phase. That is, integration is built into the design. However, it is still beneficial to bring the findings of the components together to identify an integrated set of findings. We will use adapted Triangulation Protocol to compare and contrast findings from each component, considering where they agree, disagree, or offer explanation of findings from different phases (Farmer 2006). We have used this successfully in a number of NIHR studies e.g. to bring together findings from a realist review, qualitative interview study and population survey undertaken sequentially (O'Cathain 2020).

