1 BACKGROUND

Screening for Abdominal Aortic Aneurysms (AAA)

There are 4000 deaths annually in England and Wales following Abdominal Aortic Aneurysm (AAA) rupture. Screening can pick up an AAA before it ruptures. The NHS AAA Screening Programme (NAAASP) in England was established to screen men because they are six times more likely to have an AAA than women. NAAASP has been offering screening routinely since 2009, becoming fully operational in 2013, at the cost of £14 million per year (Richards 2019). A recent analysis of outcomes of the screening programme showed that between 2009 and 2016 1.2 million men were screened, and 3000 had a large AAA and were referred for possible surgical intervention (Meecham 2021). Screening reduces AAA-related mortality and is cost-effective (Thompson 2009).

Men are invited to attend a screening clinic for an ultrasound scan in the year they turn 65.

Approximately 300,000 men are invited annually. Uptake is high, at around 80%. Men are told the outcome at screening. If an AAA is detected, the recommended treatment depends on its size. The outcome of screening and its associated treatment is:

- No aneurysm – no further screening or treatment (98% of men screened).
- Small AAA (3 to 4.4cm) – ultrasound scans every year (1% of men screened).
- Medium AAA (4.5 to 5.4cm) – ultrasound scans every 3 months (0.5% of men screened).
- Large AAA (5.5cm or more) – surgery to stop it bursting is usually recommended.

Currently 15,000 men with small and medium AAAs are 'in surveillance', having scans annually or every three months.

Evidence about psychological consequences of screening

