Researchers propose that the psychological harms of screening are not considered enough and that the attention they receive depends on the screening programme (DeFrank 2014). Studies assessing psychosocial effects of AAA screening have used generic psychological health measures such as the SF36 which may not be sensitive to screening-related harms (DeFrank 2014). The exception to this is a recently published survey of 250 men detected with AAA through screening compared with 500 men with normal screens in Sweden (Damhus 2021). This research group used the Consequences of Screening in AAA tool (Brodersen 2018) and found that men with AAA had more negative consequences in 10/13 scales in Part 1 and 4/5 scales in Part 2 of the tool e.g. feeling more anxious. Damhus and colleagues highlighted that they did not consider how negative issues changed over time, or determine the characteristics of men with higher levels of negative consequences.

It is also the case that the current evidence base focuses on measuring and understanding psychosocial consequences of AAA screening rather than on developing or evaluating interventions to address these.

Evidence about exiting the surveillance programme

There is a limited 'Exit Strategy' for men in surveillance. There is a Standard Operating Procedure for men with small or non-progressing AAAs to be discharged after 15 years (when they reach 80 years of age). This is not in operation currently because men have only been 'in surveillance' for a maximum of 8 years due to the start date of the screening programme. It will be relevant in 2028 when it will start affecting thousands of men. Otherwise men in surveillance remain there unless they die, or decline screening, or develop a large AAA and are referred for surgery. While 'in surveillance' they may develop conditions (such as cancer and cardiovascular disease) that mean they are unfit for surgery if they develop large AAAs. That is, they remain in surveillance even though they cannot have treatment. Men's health is not checked in the screening programme. They are offered appointments with a Vascular Nurse Specialist for support and guidance when they enter surveillance and again if they change to three-monthly surveillance. There is no other input.

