We will draw three samples from the included centres: 400 men who joined surveillance in the previous year, a random sample of 400 men who have been in annual surveillance for 1-8 years, and 400 men in three-monthly surveillance. This sampling strategy ensures we include large numbers of men who are potentially most likely to be anxious. Discussions with PPI drew attention to the important group of men just below the threshold for surgery (5-5.4cm), and the Lead Nurse for NAAASP has identified this group as being in particular need of help. We will have no exclusion criteria.

We will start the process in a single centre as an informal pilot to gauge the response rate and identify ways to increase response rates in other centres if necessary. If we obtain a 60% response rate after one reminder, then we will have a sample of 720 responses (see sample size calculation below). A response rate of 50% would give us 600 responses. If all the questionnaires are sent at the same time, then men will be at different times post-screening, allowing us to compare rates of negative consequences at different times post-screening.

Identification of participants

Each screening centre will identify around 100 to 200 men from the 3 samples listed above (depends on the size of the Centre). Most men have given permission to be approached for research as part of the screening service. The Centre staff will remove men who have asked not to be approached for research and create a list of men who have given permission to be approached. The list will have the men's name and address (including postcode). The screening centre staff will send it using a secure data transfer process to the researchers at the University of Sheffield.

Each screening centre will require Caldicott approvals to send the data to the University of Sheffield. Caldicott permissions can only be applied for once NHS ethics and HRA approvals are in place.

Data collection

The research team will post a covering letter, the questionnaire and a reply-paid envelope to each man on the list. The letter will also include a web address (and possibly a QR code) to access the survey for any men that want to complete it online. We will send one reminder after two weeks.

Analysis

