7.1.2 Exclusion criteria

There are no exclusion criteria

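### The 1-8 year limit on the WP1 annual-surveillance stratum rests on an outdated maximum, so men on annual scans for more than 8 years fall in no stratum

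*Protocol*

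**What the plan says.** Section 5, Work Package 1, survey of men in surveillance (Sample), defines three groups of 400. The first is recent entrants, with up to a year since joining. The second is described as "a random sample of 400 men who have been in annual surveillance for 1-8 years". The third is made up of men scanned every three months. Only the second has an upper limit on duration.

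The limit agrees with Section 1 (exiting the surveillance programme), which says "men have only been 'in surveillance' for a maximum of 8 years due to the start date of the screening programme". The same paragraph describes a 15-year discharge procedure and says of it: "It will be relevant in 2028 when it will start affecting thousands of men".

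Section 1 also dates the programme: "NAAASP has been offering screening routinely since 2009, becoming fully operational in 2013". The Study Summary starts the study on 1 October 2022, and Appendix 2 puts the WP1 survey at month 6. The protocol version is dated 4 April 2023.

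The WP1 analysis compares scale scores by number of years in surveillance, among other characteristics. Section 9.1 (Impact) intends to report the percentage of men with small AAAs who have psychosocial consequences, to inform a screening-policy decision about men with smaller aortas.

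**The concern.** The limit seems meant to take in everyone past the first year, on the belief that nobody had been in surveillance longer than 8 years. If that belief was out of date when the lists were drawn, the limit stops being a description and becomes a restriction. A man on annual scans for more than 8 years is not a recent entrant, is outside the 1-8 year window and is not on three-monthly scans, so he has no chance of selection.

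Two results are affected. The comparison by years in surveillance would have no data beyond 8 years for annual men, who are the small-AAA group. The small-AAA level that Section 9.1 wants to report would leave out the longest-standing members of that group. The weighting mentioned in the WP1 analysis addresses differential non-response and cannot restore men who were never eligible for selection. The WP1 interviewees are chosen from survey respondents, so the gap carries into that component.

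**Working it through.** **1. Survey date.** Section 8.2 equates month 23 with August 2024, so month 1 is October 2022. Month 28 is then January 2025, which agrees with the Study Summary. Month 6 is March 2023.

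**2. Can the 8-year maximum be reproduced?** The Background's 2028 date less 15 years gives first entry in 2013, the year of full operation. 2013 + 8 = 2021, so the figure fits 2021 with a 2013 start. With a 2009 start it fits 2009 + 8 = 2017. Neither is the survey year.

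**3. Maximum duration on 1 March 2023.**

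| Entry counted from | Years to 1 March 2023 |
|---|---|
| 1 January 2009 | 14.2 |
| 31 December 2009 | 13.2 |
| 1 January 2013 | 10.2 |
| 31 December 2013 | 9.2 |

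Using the version date of 4 April 2023 adds about 0.1 year. The conclusion does not depend on the month-6 schedule: from 31 December 2013 to the first day of the study, 1 October 2022, is already 8 years 9 months.

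**4. Who is left out.** March 2023 less 8 years is March 2015. Men who entered before then and are still on annual scans fall outside all three groups.

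**5. Illustrative size.** The protocol gives no count by duration, so this step rests on assumptions. Take a constant intake I per year for T years and a constant exit rate λ, chosen so that the stock equals the 15,000 stated in the protocol:

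- I × (1 − e^(−λT)) / λ = 15,000
- share beyond 8 years = (e^(−8λ) − e^(−λT)) / (1 − e^(−λT))

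Two intakes can be taken from the protocol. The WP1 Sample text gives about 2000 new men a year. Section 1 gives 300,000 invited, 80% uptake, 1% small and 0.5% medium AAAs: 300,000 × 0.80 × 0.015 = 3,600.

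| I per year | T (years) | λ | Men beyond 8 years | Share of 15,000 |
|---|---|---|---|---|
| 2000 | 9.2 | 0.046 | 1,616 | 11% |
| 2000 | 10.2 | 0.064 | 2,466 | 16% |
| 2000 | 13.2 | 0.096 | 3,815 | 25% |
| 2000 | 14.2 | 0.102 | 4,063 | 27% |
| 3,600 | 9.2 | 0.203 | 757 | 5% |
| 3,600 | 10.2 | 0.213 | 1,155 | 8% |
| 3,600 | 13.2 | 0.228 | 1,766 | 12% |
| 3,600 | 14.2 | 0.231 | 1,870 | 12% |

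Rows with T of 13-14 years are an upper end, because they assume full intake from 2009 although the programme was not fully operational until 2013. All shares are of all men in surveillance, including three-monthly men to whom the limit does not apply.

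**6. Sample size.** Section 7.2.1 compares small with medium AAAs: difference 5, SD 21.84, two-sided 5%, 80% power. n per group = 2 × (1.960 + 0.842)² × 21.84² / 5² ≈ 300, which reproduces the stated figure. Duration does not enter it.

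**The case against.** The strongest reply is that 1-8 years was simply shorthand for everyone past the first year, written when 8 was the maximum, and that no exclusion was intended. That is probably right about intent. But screening centres identify the men from these group definitions, and the current wording gives them no reason to list an annual man with nine years in surveillance.

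Several stronger readings are tempting but are not supported:

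- **That long-duration men are missing altogether.** The three-monthly group has no duration limit, so long-standing men with medium AAAs can be sampled and enter the regression.
- **That the duration trend is biased.** Restricting the range of a predictor does not by itself bias a correctly specified slope. It prevents statements about annual men beyond 8 years and costs some precision. A pooled level would not describe the programme unweighted in any case, because recent entrants and three-monthly men are deliberately over-sampled.
- **That the limit breaches the eligibility section.** Section 7.1.2 says "There are no exclusion criteria", but a stratum definition is not an eligibility criterion, and Section 7.1.1 says that different parts of the study need men at different stages. The tension is secondary.
- **That men nearest to exit are lost to the exit work.** Exit preferences belong to WP2, whose interviews and survey have no duration limit.
- **That the 2028 date is wrong.** It equals 2013 + 15 and is tied to when thousands of men are affected, not to the first man reaching 15 years.

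**Conclusion.** The point holds as a coverage gap confined to men still on annual scans after more than 8 years. It follows from the protocol's own dates: the true maximum at the survey is about 9-10 years from 2013, or up to about 13-14 from 2009. The survey as written would give no information on those men, which limits the years-in-surveillance comparison and the reported small-AAA level for that group.

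The number affected is not known. If intake and exit rates are constant and the stock is 15,000, men beyond 8 years are about 11-16% of all men in surveillance (2013 start) or 25-27% (2009 start, an upper end) at 2000 entrants a year. At 3,600 a year they are about 5-8% or 12%. How many are on annual scans cannot be derived from the protocol. The 300-per-group calculation stands. This is a modest defect, most likely an outdated figure rather than a deliberate choice, and worth correcting because the correction is so cheap.

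**What to change.** In the WP1 Sample text and in the instruction to screening centres, define the second group as men in annual surveillance for more than 1 year, with no upper limit, still drawn at random and still 400 invitations. In Section 1, reconcile the statement of an 8-year maximum with the 2009 and 2013 programme dates and the actual survey date. The 2028 date need not change.

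The cost is one phrase in the sampling definition and one corrected sentence in the Background, with no extra men and no change to the sample size. If lists have already been drawn with the 8-year limit, the report should say that the annual group covers 1-8 years only and restrict its statements on duration and small-AAA level accordingly.

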The psychosocial consequences of screening are often measured for different screening programmes so that harms do not outweigh benefits (Ericsson 2017). Experiences vary enormously by condition and screening programme, so it is important to consider what is known about AAA screening specifically. A systematic review of the psychological harms of being labelled as having AAA identified five quantitative studies and three qualitative studies (Cotter 2017). Both the qualitative and quantitative studies found at least moderate levels of psychological harm from recent diagnosis. Qualitative studies found that men suffered shock, anxiety, fatalism, general distress, burden from protecting others from worrying, guilt, helplessness, and uncertainty (Pettersson & Bergbom 2013; Gunasekera 2013; Hansson 2012) even though they were glad they were being monitored (Pettersson & Bergbom 2013). Later qualitative studies have also found this heightened anxiety and described

how it impacts on men's health-related quality of life (HRQoL)(Brodersen 2018, Aber 2020a). These psychosocial issues also affect their partners' HRQoL (Ericsson 2020). A recently published narrative review focused on 11 quantitative studies of HRQoL for men being screened for AAA (Ericsson 2019). Those in surveillance had lower HRQoL compared to those with negative scans and the general population. A quantitative study in the UK showed that mental health was worse in those diagnosed with AAA compared with those with negative screens; this difference disappeared after 12 months (Bath 2018) although a generic rather than specific measure of HRQoL was used. This means that each year approximately 2000 men enter surveillance and have reduced mental health at least in the first year. This has led researchers to conclude that counselling may be needed (Bath 2018).

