All data will be entered into SPSS for analysis and the scores calculated for the two AAA-specific scales, PCSQ and EQ5D-5L. Mean scores for each AAA-specific scale and PCSQ will be compared by size of AAA, perceived rate of growth of AAA, months since last screening, number of years in surveillance, socio-demographic characteristics and EQ5D-5L. It will be a simple analysis, first comparing unadjusted means by group using a t-test or ANOVA. Then we will undertake multiple linear regression on each AAA-specific scale and the PCSQ to identify the set of characteristics of the AAA or the man that predict negative consequences. Higher rates at particular time periods, or in particular groups of men, with help to focus the proposed intervention on where it can help the most. This information will also be useful to other research groups wanting to reduce the negative consequences of AAA surveillance. The analysis will be led by AOC who has a Masters in Social Statistics, with advice from SR who is experienced at analysing the e-PAQ suite of questionnaires.

We will check for non-response bias by age and level of social deprivation (using postcode to identify IMD quintile). We may weight the sample to compensate for differential non-response.

2. Qualitative interviews with men in surveillance with psychosocial consequences (and their partners/family members)

Sample

We will undertake a qualitative interview study with 20-24 men 'in surveillance' and reporting psychosocial consequences in the survey above. We will sample men with different sizes of AAA and feeling anxious at different times of the surveillance trajectory. We will attend to inclusivity by aiming for maximum diversity in terms of age, social deprivation, ethnicity, disability and multiple disadvantage. We will also interview partners (or key family members) with agreement of the men (n=12-20). We will explore causes of any anxiety in family members, the trajectory of anxiety over time, and views on different options for managing problems. We will interview men and their partners/family separately or together based on their preferences.

Identifying the sample

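### Months since last scan measures time since diagnosis in new men on annual scans but scan-cycle position in established men, so comparing by it mixes the two effects

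*Protocol*

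**What the plan says.** Section 1 (Background) gives the surveillance schedule. Small aneurysms have "ultrasound scans every year (1% of men screened", and medium aneurysms have "ultrasound scans every 3 months (0.5% of men screened". The same section cites a UK study in which mental health was worse in diagnosed men than in screen-negative men, and "this difference disappeared after 12 months".

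Section 5, Work Package 1, survey of men (Sample) draws three groups of equal size. The new entrants are "400 men who joined surveillance in the previous year". The established group on yearly scans is "a random sample of 400 men who have been in annual surveillance for 1-8 years". The last group, scanned more often, is "400 men in three-monthly surveillance". The section then says that, if all questionnaires go out together, "men will be at different times post-screening, allowing us to compare rates of negative consequences at different times post-screening".

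The questionnaire asks for both the date of the last screen and the length of time in the programme. The Analysis paragraph compares mean scores by months since last screening and, separately, by years in surveillance, first unadjusted and then in a multiple linear regression. It states no split or interaction between new and established men. It gives the purpose of the time comparison as "Higher rates at particular time periods, or in particular groups of men, with help to focus the proposed intervention".

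**The concern.** A man who joined in the past year and is scanned annually has had one scan, the one that found the aneurysm. For him, time since last scan and time since diagnosis are the same number. For a man in his second to eighth year of annual scans, time since last scan says where he is between two routine scans. Both values run from 0 to 12 months under one variable name.

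The protocol's own evidence makes an improvement over the first 12 months after diagnosis plausible. If it occurs, new men score worse at low values of the variable and better at high values, and a comparison over both groups shows a decline after a scan even if routine scans have no effect. The two explanations point to different intervention timings, around each routine scan or around entry to surveillance, and the survey is meant to inform that choice.

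**Working it through.** **1. The plan's own figure.** Section 7.2.1 gives SD 21.84, a meaningful difference of 5 points, 5% level and 80% power. Taking the test as two-sided, n per group = 2 × (1.96 + 0.84)² × 21.84² / 5² ≈ 300. This reproduces the stated 300 per group. It concerns small versus medium aneurysms, not time since scan. It is used here only for the SD and for 5 points as a yardstick.

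**2. What the time variable means in each group**

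| Group | Range, months since last scan | Meaning |
|---|---|---|
| New, annual scans | 0–12 | time since diagnosis |
| New, three-monthly scans | 0–3 | position in 3-month cycle |
| Established, annual | 0–12 | position in yearly cycle |
| Three-monthly sample | 0–3 | position in 3-month cycle |

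The identity in the first row follows from the schedule. It does not extend to new men with medium aneurysms.

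**3. Size by direct arithmetic.** Assumptions not in the documents: an excess of D points at diagnosis falling in a straight line to zero at 12 months, no true scan-cycle effect, even spread of months within each range, and all new men on annual scans. From the plan: three equal strata and a 50% response, so 200 replies each if response is equal across strata.

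With a separate level for each stratum, the common slope is the average of the stratum slopes weighted by the variance of months. That variance is 12²/12 = 12 for a 0–12 range and 3²/12 = 0.75 for a 0–3 range. The slope per 12 months is −D in new men and 0 elsewhere:

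common slope = −D × 12 / (12 + 12 + 0.75) = −0.485 D

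For D = 5, 10 and 15 this is −2.4, −4.8 and −7.3 points per 12 months, where the true scan-cycle slope is 0.

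**4. Simulation with the listed predictors.** Least squares on months since last scan, years in surveillance and scan interval, with residual SD 21.84:

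| Assumed excess at diagnosis | 5 | 10 | 15 |
|---|---|---|---|
| False decline per 12 months, all new men annual | 2.3 | 4.7 | 7.1 |
| False decline, one third of new men three-monthly (assumed) | 1.9 | 3.5 | 5.5 |
| Established annual men only | about 0 | about 0 | about 0 |

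In the second row, a false scan-cycle effect is declared in 7% of surveys at the 5-point excess, rising to 26% at 15 points, against a nominal 5%. Exponential rather than linear recovery makes the biases about 10–25% smaller.

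**5. Why years in surveillance does not help.** Whole years do not vary within the first year. A linear term is fixed mainly by the established men's longer range and cannot follow a decline confined to year one. Coding years as whole numbers or as a continuous value moves the 10-point result (all new men annual) only between 4.9 and 4.2. Adding a first-year indicator leaves it unchanged, because it shifts the level and not the slope.

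**6. Precision within one stratum.** For 200 men spread over 0–12 months, the SD of months is 12/√12 = 3.46. SE per 12 months = 12 × 21.84 / (√200 × 3.46) ≈ 5.35, or about 5.4 in the simulation. Detectable at 80% power: 2.80 × 5.35 ≈ 15 points over the cycle. A 60% response (240 men) gives SE 5.35 × √(200/240) ≈ 4.9 and about 13.7 points.

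**The case against.** The strongest reply is that the Analysis paragraph lists variables without fixing their coding, subgroups or interactions, which a statistical analysis plan may settle. Both time variables are collected and the sampled strata allow the right analysis. This stands to the extent that a reader might infer that the protocol commits to one pooled coefficient; it does not say so. What remains is that Section 5 states that a single mailing permits a comparison by time after screening, and names one variable for it that means different things in two of its three samples.

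A second reply is that the size is assumed. This stands. No document gives an excess at diagnosis on these scales, and the 12-month finding comes from a generic measure and a comparison with screen-negative men. At a 5-point excess the bias is less than half the protocol's meaningful difference.

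Third, a reader might infer that the survey will put the intervention at the wrong time. The documents do not support that. Men are also interviewed about different points in the surveillance trajectory, and the second co-design workshop considers when the intervention would be offered. Means by years in surveillance would also show higher scores in new men directly.

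Fourth, splitting costs accuracy. In one run with 200 per stratum, total error (root mean square) at a 5-point excess was 4.5 for the pooled estimate and 5.5 for established annual men alone; at 10 points it was 5.9 against 5.3. So the split is not always more accurate. It does estimate a defined quantity, and its imprecision is visible in the interval.

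**Conclusion.** The concern holds in a limited form. For new men on annual scans, time since last scan is time since diagnosis, and the planned comparison mixes any recovery from diagnosis into the scan-cycle effect. Adjusting for years in surveillance or scan interval does not separate them. With no true scan-cycle effect, the spurious decline is about 2 points per 12 months for a 5-point excess at diagnosis and 3.5 to 4.7 for a 10-point excess, depending on how many new men are on three-monthly scans. These figures rest on an assumed excess, a linear fade to zero at 12 months, and equal response across strata. New men on three-monthly scans are outside the identity. The consequence is a risk of misreading when men are most affected.

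**What to change.** In Section 5, Work Package 1 survey, Analysis, state that time trends will be reported within the three sampled strata:

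- **Joined in the previous year:** time since joining surveillance (time since diagnosis), from the time-in-programme question, adjusted for scan interval.
- **Established annual:** months since last scan, over 0–12 months.
- **Three-monthly:** months since last scan, over 0–3 months.

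Any pooled regression should carry these stratum-specific terms in place of a single months term. A simple interaction of months with first-year yes/no is not enough. It puts established annual and three-monthly men on one slope and keeps two meanings of the variable among new men. When one third of new men are three-monthly, it leaves a residual bias of 0.8 to 2.2 points per 12 months in the simulation.

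Limit the Sample sentence on comparing times after screening to match, and describe the time trends as exploratory.

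The cost is a few sentences and no new question, provided that time in the programme is recorded in months for new men. The real price is precision: an SE of about 5.4 points per 12 months with 200 replies per stratum, so that differences much smaller than about 15 points over the yearly cycle will usually be missed.
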